c. Analysis of Co-Primary Endpoints. We hypothesize that topiramate will reduce the rate of deterioration of IENFD over the full follow-up period. Hence the primary analysis of the IENFD will compare the mean IENFD slope between the treatment and control groups under a longitudinal model with fixed effects for baseline IENFD, age, baseline BMI randomization stratification group, follow-up time (as a continuous variable), and the interaction between treatment assignment and follow-up time. Inclusion of baseline IENFD as a covariate will increase statistical power in a similar fashion as adjustment for the baseline level of the outcome in a conventional analysis of covariance. Expressed mathematically, the longitudinal model for IENFD is: $Y_{it} = \alpha_0 + Y_{i0} \beta_0 + \text{Age} \beta_1 + [\text{BMI Group}] \beta_2 + Y_{i0} \times \text{time}_{ij} \times \beta_3 + T_i \beta_4 + \text{time}_{it} \beta_5 + T_i \times \text{time}_{it} \beta_6 + \varepsilon_{it}$, $\text{Var}(\varepsilon) = \Sigma$, $i = 1, 2, \dots, N$, $t = 0, 1, 2, 3$, where Y_{it} denotes the IENFD measurement for patient i at visit t , with $t = 0$ representing the baseline visit so that Y_{i0} is the baseline IENFD, T_i denotes the randomized treatment group for the i th patient (with $T_i = 1$ for the topiramate group, and $T_i = 0$ for the control group), time_{it} denotes the time of the t^{th} IENFD measurement for patient i , $T_i \times \text{time}_{it}$ denotes the treatment by time interaction, and the ε_{it} denote residuals of the IENFD measurements which are assumed to be normally distributed with a covariance matrix Σ which is described below. The coefficient β_6 represents the effect of the topiramate treatment on the mean IENFD slope over time. We will use a general unstructured covariance model for Σ ⁷⁶ so that the full model represents a special case of the linear mixed model^{76,77} that allows for all possible correlations among the residuals among the IENFD measurements. When the number of time points is small relative to the number of subjects as is the case for IENFD in this proposal, the general unstructured covariance model is widely used in randomized trials because it provides essentially identical statistical power to that obtained under less general covariance models while avoiding the need for post-hoc modifications to satisfy modeling assumptions⁷⁶. Estimates of the model coefficients and standard errors will be obtained by restricted maximum likelihood estimation (RMLE)⁷⁸.

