the NQOL-DN to 2 years, linear contrasts will be constructed to estimate the effect of the treatment on the early change in the NQOL-DN to 16 weeks, and on the longer-term NQOL-DN slope after 16 weeks. Expressed mathematically, the mixed effects model for the NQOL-DN is: $Y_{it} = \alpha_0 + Y_{i0} \beta_0 + \text{Age} \beta_1 + [\text{BMI Group}] \beta_2 + Y_{i0} \text{timlo}_{it} \beta_3 + Y_{i0} \text{timhi}_{it} \beta_4 + T_i \beta_5 + \text{timlo}_{it} \beta_6 + \text{timhi}_{it} \beta_7 + T_i \times \text{timlo}_{it} \beta_8 + T_i \times \text{timhi}_{it} \beta_9 + \varepsilon_{it}$, $\text{Var}(\varepsilon_{it}) = \Sigma$, $i = 1, 2, \dots, N$, $t = 0, 1, 2, \dots, 6$, where Y_{it} denotes the NQOL-DN measurement of the i^{th} patient at visit t , $\text{timlo}_{it} = \min(0, \text{time}_{it} - 16 \text{ weeks})$ and $\text{timhi}_{it} = \max(0, \text{time}_{it} - 16 \text{ weeks})$ represent linear spline terms in follow-up time, and the remaining terms are analogous to those defined in the model for the IENFD described above. Accounting for separate slopes in the first 16 weeks and the subsequent 80 weeks, the primary linear contrast defining the treatment effect on the mean change to 2 years is $4 \times \beta_8 + 20 \times \beta_9$. Due to the relatively large number (6) of follow-up measurement times for the NQOL-DN, an unstructured covariance model may lead to inefficient estimation⁷⁶, and a relatively parsimonious covariance model will be used to limit the number of unknown parameters to be estimated⁷⁶. Standard covariance models to be considered include models with random intercepts and slopes combined with an autoregressive or Toeplitz covariance matrix for the residuals around the underlying trajectories⁷⁹⁻⁸¹. The covariance model will be selected from a pre-specified collection of potential models by comparing BIC statistics under maximum likelihood estimation⁸¹. After selection of the covariance model, final statistical inferences will be performed using restricted maximum likelihood estimation as in the analyses of the IENFD outcome.

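### Section 10.c gives the primary IENFD model in two incompatible forms, and the printed equation, with baseline as both outcome and covariate, has no REML solution

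*Combined protocol and SAP*

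**What the plan says.** All references are to section 10 of the protocol.

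- **Prose (10.c).** The fixed effects are baseline IENFD, age, BMI stratum, "follow-up time (as a continuous variable), and the interaction between treatment assignment and follow-up time". Treatment enters only through the interaction.
- **Equation (10.c).** It contains "T_i \beta_4 + \text{time}_{it} \beta_5 + T_i \times \text{time}_{it} \beta_6", so treatment also has a main effect, and "Y_{i0} \times \text{time}_{ij} \times \beta_3", a baseline × time term. Neither is in the prose list.
- **Outcome rows.** The index is "t = 0, 1, 2, 3$, where Y_{it} denotes the IENFD measurement for patient i at visit t". Visit 0 is defined as baseline, and Y_i0 is also a covariate with coefficient β0. Σ is unstructured and estimation is by REML.
- **Target.** Topiramate is hypothesised to "reduce the rate of deterioration of IENFD over the full follow-up period", and β6 is named as the effect on the mean slope. The baseline covariate is meant to add power "in a similar fashion as adjustment for the baseline level of the outcome in a conventional analysis of covariance".
- **Power (10.e).** 125 patients give 80% power for a slope difference of 0.47 fibers/mm/year, from biopsies at baseline and weeks 32, 64 and 96 with 4% loss per 32 weeks. Variance components are mentioned but not printed.
- **NQOL-DN (10.c).** The layout is the same, with t = 0 to 6 and Y_i0 as covariate, yet the text speaks of a "relatively large number (6) of follow-up measurement times for the NQOL-DN". It says "the primary linear contrast defining the treatment effect on the mean change to 2 years is" 4β8 + 20β9.
- **Go/No-Go (10.f).** The rule takes the IENFD group difference against cut-offs of 0.30 and −0.22 fibers/mm/year.

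**The concern.** This model is the primary test of a co-primary endpoint and supplies the IENFD input to the Go/No-Go rule. The analyst must decide which rows are outcomes and whether treatment has a main effect, and no passage says whether prose or equation governs. The choices are not equivalent. One cannot be fitted by the stated method, and another changes what β6 measures. If the choice is made after unblinding, the primary analysis is no longer prespecified.

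**Working it through.** **1. The plan's own figures.** The stated IENFD power implies SE(β6) = 0.47/(1.960 + 0.842) = 0.47/2.802 = 0.168. It cannot be reproduced further without the variance components. The adjacent NQOL-DN figure does reproduce. The SD after baseline adjustment is 16.4/√(2 × 0.4) × √(1 − 0.36) = 14.7. With 125 × 0.88/2 = 55 per arm, power at 7.9 points is 80.6%.

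**2. Literal reading: outcomes at t = 0, 1, 2, 3.** At t = 0 every time term vanishes, leaving

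Y_i0 = α0 + β0·Y_i0 + β1·Age + β2·BMI + β4·T_i + ε_i0.

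Setting β0 = 1 and the other four coefficients to 0 makes every ε_i0 zero. Σ is unstructured, so the time-0 variance Σ00 is free to shrink, and the restricted log-likelihood behaves like −((125 − 5)/2)·ln Σ00. It rises by 60 × 2.3026 = 138.16 per tenfold fall, without limit. In one simulated trial of 125 the rise was 138.15 to 138.16. On the same data both versions restricted to t = 1, 2, 3 converged. In the limit β6 stays finite, but age, BMI and the baseline main effect no longer adjust anything.

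**3. Notation reading: t = 0 only defines Y_i0; outcomes at t = 1, 2, 3.** The likelihood is bounded. With β4 in the model each arm has its own level, so β6 uses only the change from week 32 to week 96. Without β4 the arms share a mean at time 0 and β6 is the slope difference from randomisation. In the simulated trial, β6 was 0.433 (SE 0.182) with the prose terms and 0.288 (SE 0.284) with the equation terms.

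**4. Early effect (illustration).** A benefit of 0.47 × 96/52 = 0.87 fibers/mm, complete by week 32 and then held, gives treatment differences (0.87, 0.87, 0.87) at follow-up. β4 absorbs this exactly, so expected β6 = 0. The prose model gives 0.45–0.57 fibers/mm/year over the grid in step 5.

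**5. Power at a true difference of 0.47 (assumed variances).** Setting: 125 patients, 1:1, the section 10.e schedule and losses; random intercept and slope, uncorrelated, plus residual; intercept/residual variance ratio 0.5 to 6; within-patient share of the four-visit slope variance 100% to 5%.

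| Stated 80% belongs to | β4 kept | Prose model |
|---|---|---|
| Four-visit slope model (SE 0.168) | 42–76% | 80–94% |
| Prose model | 29–76% | 80% |

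In the first row, β4-kept power is 42, 55, 65, 73 and 76% at within-patient shares of 100, 50, 25, 10 and 5%. The SE ratio, β4 kept to prose, is 1.05–1.99. In the limit of step 2 power is 80–94%. Allowing intercept–slope correlations from −0.5 to 0.5 widens β4-kept power to 42–84% (first row) and 29–79% (second row).

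**6. Go rate with no effect on either endpoint.** Inputs: the section 10.f cut-offs; correlation 0.30 on the benefit scale; NQOL-DN SE = 7.9/2.802/2 = 1.41 points/year. At IENFD SE 0.168 the rate is 5.2%, against a stated maximum of 5%. With β4 kept it is 5.8–14.0% (first calibration) or 5.8–19.2% (second).

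**7. NQOL-DN contrast.** The early spline term is min(0, time − 16 weeks), which is zero at every nominal follow-up visit. The 11-column design has rank 11 with baseline rows and 8 without, so on follow-up rows β8 is not estimable. Spreading visits over the ±7-day window restores rank 11, but only through small timing differences. The SE of 4β8 + 20β9 is then about 68–102 points, against 2.3–2.5 for β5 + 20β9 (residual SD 14.7; assumed within-patient residual correlation 0.3–0.7).

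**The case against.** The best defence is that the two defects do not both do harm on any one reading. On the literal reading β4 is driven to 0, β6 stays finite and power in the limit is at or above plan, so the failure is one of fitting, which an analyst would notice. On the notation reading the likelihood is bounded. All the quantified IENFD harm comes from dropping the time-0 rows while keeping β4, and the prose list, the stated target and the power design all point away from that.

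The worst figures also need no between-patient slope variance, although section 10.e mentions variance components for trajectories. At within-patient shares of 5–10%, β4-kept power is 73–76% (first calibration) and the Go rate is about 6%. The early-effect argument borrows from weight-loss timing in section 2.4, which is not IENFD. The NQOL-DN model plans a parsimonious covariance, so step 2 does not carry over to it, and its contrast is estimable with the printed baseline rows.

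Much of this stands. Most repairs keep target and power, the size of the loss is uncertain, and the early plateau is only an illustration. The excess of 5.2% over 5% is not caused by this defect. What does not stand is that the intended model is clear. The analysis-of-covariance wording and the count of six follow-up times support follow-up rows only, and an analyst who then keeps every printed term arrives at the version with the wrong target.

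**Conclusion.** The primary IENFD model is wrong as written and should be corrected before unblinding. Three conclusions need no assumed variances: prose and equation differ in two terms; the literal equation has no REML maximum; and on follow-up rows with β4 kept, β6 is the week 32–96 slope difference, not the slope over the whole of follow-up. Nor does the direction of the precision loss: the prose treatment terms are nested in the β4 version, so under the same variances β4 cannot improve precision.

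The size is conditional. With β4 kept, power for 0.47 fibers/mm/year lies between 29% and 84% across the two calibrations and all the correlations considered, a loss of 1 to 52 points against the prose model. The null Go rate is 5.8–19.2% at zero intercept–slope correlation. The loss is small if patients' slopes vary widely and large if they do not.

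**What to change.** State the outcome rows and treatment terms once, and edit prose and equation together. Either:

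- **(a)** use outcomes t = 1, 2, 3, keep Y_i0 and Y_i0 × time as covariates, delete T_iβ4, and add Y_i0 × time to the prose list; or
- **(b)** use a constrained longitudinal model with baseline in the outcome vector, a common mean at time 0 and no Y_i0 covariate, and rewrite the sentence on baseline adjustment to match.

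Say explicitly that β6 is the slope difference from randomisation, and restate the power for the chosen model with its variance components.

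Correct the NQOL-DN model in the same edit. If only follow-up rows are outcomes, T_iβ5 must stay there, the early-spline terms drop out as redundant, and the week-96 contrast becomes β5 + 20β9 in the plan's 4-week units.

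The cost is wording; no data or visits are added. Both IENFD options fix the time-0 treatment difference at zero, which randomisation justifies. Option (a) also makes the treatment difference proportional to time, as the plan's prose already does: in the step 4 scenario it returns 0.45–0.57 where the average to week 96 is 0.47. Under (a), patients without a follow-up biopsy, about 4% on the plan's attrition, contribute nothing.

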
Topiramate may have direct effects on QOL that are independent of CSPN progression and which may occur shortly after treatment initiation, as well as longer term effects that result from effects of topiramate on neuropathy progression. Accordingly, the primary analysis of the NQOL-DN will compare the total mean change in the NQOL-DN from baseline to 2 years between the treatment and control groups under a longitudinal model that includes linear spline terms to allow separate mean slopes during the first 12 weeks after randomization and from 12 weeks to the end of follow-up. Age, baseline BMI group and baseline NQOL-DN will be treated as a covariates to increase statistical power. In addition to the primary comparison of the total mean change in

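### The NQOL-DN co-primary spline has a 12-week knot in the prose but a 16-week knot in the equation and contrast, and the time unit of the contrast weights is not stated

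*Combined protocol and SAP*

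**What the plan says.** All of this is in the combined protocol and SAP, Section 10, paragraph c, in the part on the NQOL-DN.

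- **Estimand.** The primary analysis is to "compare the total mean change in the NQOL-DN from baseline to 2 years" between the arms.
- **Knot in the prose.** The linear spline is to allow "separate mean slopes during the first 12 weeks after randomization and from 12 weeks to the end of follow-up".
- **Knot in the equation.** The two spline terms, timlo and timhi, are the negative and positive parts of time minus 16 weeks.
- **Secondary contrasts.** Their targets are "the effect of the treatment on the early change in the NQOL-DN to 16 weeks, and on the longer-term NQOL-DN slope after 16 weeks".
- **Primary contrast.** Its derivation opens with "Accounting for separate slopes in the first 16 weeks and the subsequent 80 weeks". From those two lengths the plan obtains 4β8 + 20β9, where β8 and β9 are the treatment interactions with timlo and timhi. It calls this sum "the primary linear contrast defining the treatment effect on the mean change to 2 years".

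Section 6.5 and Appendix A place the first scheduled post-baseline NQOL-DN at week 16. Paragraph c counts six follow-up measurements, which are weeks 16, 32, 48, 64, 80 and 96. Paragraph f compares the NQOL-DN result with cutoffs in points per year: 2.97 for benefit and 2.70 for harm.

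**The concern.** The two knots cannot both be right, and nothing in the documents reconciles them. This is the specification of the estimator for a co-primary endpoint, not background text. The spline is there because topiramate may act on quality of life soon after it is started. If the wrong knot met the printed weights, an early effect is where the estimate would be furthest off.

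The weights raise a second question. The knot is written in weeks, but 4 and 20 are not numbers of weeks. The reader has to infer the unit. The Go/No-Go rule works on point estimates in points per year, so the scale of the contrast matters there even though it does not matter for a test.

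**Working it through.** **1. The plan's contrast.** For a knot at k over 96 weeks, timlo rises by k and timhi by 96 − k. The treatment effect on the change to week 96 is therefore kβ8 + (96 − k)β9 with time in weeks.

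- k = 16: 16β8 + 80β9. In 4-week units, 16/4 = 4 and 80/4 = 20, which is the printed contrast.
- k = 12: 12β8 + 84β9. In 4-week units, 12/4 = 3 and 84/4 = 21, which is not the printed contrast.

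The comparison of ratios does not depend on the unit: the printed ratio is 1:5, and a 12-week knot needs 1:7.

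**2. The prose knot with the printed weights.** Let D16 and D96 be the treatment differences in change from baseline at weeks 16 and 96, with the later slope linear, the pre-treatment score taken as week 0, and no data between weeks 0 and 16. With a 12-week knot and time in weeks:

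- D16 = 12β8 + 4β9 and D96 = 12β8 + 84β9
- β9 = (D96 − D16)/80 and β8 = (D16 − 4β9)/12
- 16β8 + 80β9 = 1.333 × D16 + 74.67 × β9 = 0.933 × D96 + 0.400 × D16

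The target is D96.

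| Profile of the effect | D16 | Contrast returned | Error | If D96 = 7.9 |
|---|---|---|---|---|
| All after week 16 | 0 | 0.933 × D96 | −6.7% | 7.4 |
| Linear | D96/6 | 1.000 × D96 | 0% | 7.9 |
| Complete by week 16 | D96 | 1.333 × D96 | +33.3% | 10.5 |

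The value 7.9 is the detectable difference in paragraph e. Fitting the spline under independence, compound symmetry and AR(1) gave the same errors. The 16-week knot with 4:20, and the 12-week knot with 3:21, each return D96 exactly, because at the nominal visits the two knots describe the same set of means.

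**3. The unit.** If time is coded in weeks with the correct 16-week knot, 4β8 + 20β9 = (16β8 + 80β9)/4 = D96/4. A true 7.9 is returned as 7.9/4 = 1.98. The standard error is divided by 4 as well, so the test statistic and p-value do not change.

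**4. The annual scale.** Paragraph e equates 7.9 points over 96 weeks with 4.0 points per year, a divisor of 7.9/4.0 = 1.98, or about 2. A 52-week year would give 7.9 × 52/96 = 4.28. On the plan's scale, 7.9/2 = 3.95 clears the 2.97 cutoff, while the quartered value 1.98/2 = 0.99 does not.

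**5. Power.** Paragraph e uses an ANCOVA with one follow-up. The residual SD is 16.4 × √((1 + 0.6)/2) = 14.67, and 125 × 0.88 = 110 gives 55 per arm. The detectable difference is (1.960 + 0.842) × 14.67 × √(2/55) = 7.84, which agrees with 7.9. The knot does not enter.

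**The case against.** The strongest reply is that the −7% to +33% error belongs to an analysis that the plan never sets out. β8 and β9 exist only as coefficients on timlo and timhi, which are defined with a 16-week knot, and the sentence that introduces the contrast names 16 and 80 weeks. To make the error, an analyst would have to rebuild the spline at 12 weeks and keep weights whose own sentence contradicts that choice. The visit schedule also points to 16: week 12 is only a telephone call (Section 7.1.18). All of this stands. The 12 weeks in the prose is the outlier, and the printed contrast is arithmetically correct for its knot.

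On the unit, the reply is that Section 3 already counts in 4-week months: its attrition at 8, 16 and 24 months matches weeks 32, 64 and 96 in the Synopsis, and 4 + 20 = 24. That is a fair inference about what was meant. Section 10 does not say it, however, and it writes the knot in weeks.

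A reader might go on to infer that the Go/No-Go decision is unsound. The documents do not support that. The cutoffs rest on the design assumptions in paragraphs e and f and do not depend on the knot; only the observed estimate compared with them could move. A purely early 4.5-point effect would read as 1.333 × 4.5 = 6.0 under the mixed coding, or 2.25 against 3.00 per year with the divisor of 2. It passes 2.97 by 0.03, and only under that mixed coding.

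**Conclusion.** Wrong as written; a moderate internal inconsistency in the primary-analysis specification. The prose knot of 12 weeks conflicts with every other statement of the knot in the same paragraph.

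It would be too strong to say that the plan misstates its NQOL-DN effect by up to a third. Followed throughout with time in 4-week units, the equation and contrast estimate the intended 96-week change. The range of −7% to +33% applies only if the prose knot is coded with the printed weights. It further assumes that the week-16 effect lies between zero and the week-96 effect and that there are no data before week 16. Early and late effects in opposite directions fall outside the range. If the true profile bends at week 12, the lower end is 20/21 − 1 = −4.8%. Early-termination assessments before week 16 and the visit windows would shift these figures slightly.

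The unit point holds even if the 16-week knot is used. With time in weeks, the printed weights return one quarter of the change. The test is unaffected, but the estimate set against both the benefit and the harm cutoff would be too small.

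**What to change.** 1. In the prose of Section 10.c, change 12 weeks to 16 weeks in both places, to match the equation and the first scheduled post-baseline NQOL-DN.
2. Either state that time is measured in 4-week units, or define time in weeks and write the contrast as 16β8 + 80β9.
3. State the divisor that turns the 96-week contrast into points per year for the Go/No-Go rule. Paragraph e implies about 2; the text should say whether that or 96/52 is meant.

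The cost is two changed figures and one or two added lines. No data, visit or patient is affected. The change should be made before unblinding so that the estimator remains pre-specified.

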1.2. Secondary Objectives

The secondary aim is to evaluate clinical meaning of change in Intraepidermal Nerve Fiber Density (IENFD), and examine the relative contribution of its change to improvement in clinically meaningful outcomes.

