8. MANAGEMENT OF ADVERSE EVENTS

Extensive data regarding safety and adverse events are available from clinical trials of topiramate for epilepsy and episodic migraine. The dose of topiramate to be used in the TopCSPN Study is similar to that used for episodic migraine (50-200mg daily). Adverse events observed in randomized trials for migraine will be summarized⁶⁵. Following this summary, potentially significant adverse events observed at higher doses will be listed.

When topiramate must be discontinued for participant safety, the dose can be stopped immediately or titrated down based on the clinical judgement of the site investigator.

Adverse Events Observed at 100 mg daily of topiramate:

- Anorexia. Loss of appetite is one of the mechanisms contributing to weight loss. Most commonly anorexia is mild. In subjects complaining of intolerable anorexia, the dose will be tapered to the maximal tolerated dose.
- Fatigue. Subjects complaining of intolerable fatigue will be asked to taper the dose to the maximum tolerated.
- Memory Problems. Topiramate may cause confusion, psychomotor slowing, poor concentration, or memory loss. These symptoms are more commonly observed with rapid dose escalation. Patients complaining of intolerable memory problems, or those observed to have cognitive dysfunction sufficiently significant to warrant dose modification in the opinion of the PI will taper their dose to that maximally tolerated.
- Nausea. Subjects complaining of intolerable nausea will be asked to taper the dose to the maximum tolerated.
- Paresthesias. Paresthesias are typically mild and uncommonly lead to discontinuation. In the setting of this study, paresthesias may also be related to the underlying disease (CSPN), or nerve regeneration. There are no data suggesting topiramate causes or worsens peripheral neuropathy. Subjects experiencing increased paresthesias will be encouraged to continue to participate unless the symptom is severe enough in the opinion of the PI to warrant dose reduction.

Potentially serious adverse events noted in the package insert include:

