Given the previously stated assumptions for the analyses of IENFD and NQOL-DN as separate endpoints, and assuming a Pearson R of -0.30 between the IENFD and QOL-DN based on Boyd *et al*²⁴, numerical integration of the bivariate normal distribution implies that this global decision rule has a Type 1 error $\leq 5\%$ for an inappropriate recommendation to proceed to a full scale trial given inferiority for at least on outcome or absence of superiority for both outcomes, and Type 2 error $\leq 18\%$ for failure to recommend proceeding to the full scale trial when the stated criteria for superiority of at least 1 outcome and non-inferiority for both outcomes are satisfied.

g. Secondary outcomes. Treatment effects on continuous secondary outcomes which are either approximately normally distributed or can be transformed to approximate normality will be analyzed using linear mixed effect models similar to those described for IENFD and NQOL-DN. Generalized linear mixed models with outcome models appropriate to each outcome variable will be applied for ordered categorical outcomes measured at the scheduled follow-up visits and for continuous outcomes that cannot be transformed to achieve approximate normality. The treatment effect on the rate of falls will be estimated using negative binomial regression.

g. Evaluation of the clinical meaning of IENFD change. A major secondary objective of the TopCSPN study is to explore the clinical meaning of change in IENFD. TOPIRAMATE may

potentially affect NQOL-DN and other clinical endpoints (e.g., balance, fall risk) through *direct effects* that are independent of neuropathy progression (IENFD), or through *indirect effects*, which are mediated through a pathway that incorporates effects of the treatment on neuropathy progression based on IENFD. Using this conceptual framework, mechanistic information will be obtained from three types of analyses:

M1) Evaluation of the profile of treatment effects on the QOL-DN and other clinical endpoints in comparison to the treatment effect on the IENFD,

M2) Evaluation of regression coefficients relating changes in the QOL-DN and other clinical endpoints to the IENFD slope, controlling for treatment assignment,

M3) Evaluation of the “proportion of the treatment effect explained by the IENFD”⁸⁴ for the QOL-DN and other clinical endpoints.

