If the treatment does not affect NQOL-DN or another clinical endpoint, the M1 and M2 analyses will provide understanding of the null effect of the treatment. The evaluation of the profile of treatment effects in M1 will be performed by plotting the estimated treatment effects on each outcome with their 95% confidence intervals. Treatment effects on continuous and categorical variables will be estimated using linear or generalized linear mixed models analogous to those described in Aim 1; the treatment effect on the rate of falls will be analyzed using negative binomial regression. Concordant effects for IENFD and a particular clinical endpoint will suggest possible mediation of the treatment effect on the clinical endpoint through IENFD, whereas discordant effects will suggest IENFD did not play a major role (i.e. was not clinically relevant). Bootstrap resampling will be used to provide 95% confidence limits for ratios of treatment effects on IENFD vs. effects on the clinical endpoints.

The treatment effect estimates in the M1 analyses represent direct comparisons of randomized groups, and hence are not subject to confounding due to the randomized trial design. This is not the case for the M2 and M3 analyses, as confounding factors that jointly influence both the intermediate variables and the NQOL-DN or other clinical endpoints will lead to biased estimates⁸⁵. Failure to recognize this issue has led to confusion in prior applications of path analysis for evaluation of mediating factors⁸⁶. Thus, we will seek to identify and control for baseline and follow-up factors that may potentially influence both IENFD and NQOL-DN or other clinical endpoints in the M2 and M3 analyses.⁸⁷

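### Discordant M1 effects cannot show that IENFD change lacks clinical relevance, because M1 compares total effects and the plan allows direct drug effects

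*Combined protocol and SAP*

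**What the plan says.** Section 1.2 gives the objective: "The secondary aim is to evaluate clinical meaning of change in Intraepidermal Nerve Fiber Density (IENFD"). Section 10.1.1 adds that validating both co-primary measures for a later Phase III trial is a major secondary objective.

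Section 10, in the item on the clinical meaning of IENFD change, starts from a direct/indirect framework. Topiramate may affect NQOL-DN and other endpoints through direct effects "that are independent of neuropathy progression (IENFD), or through" indirect effects mediated by IENFD. Item c says the same of quality of life: "Topiramate may have direct effects on QOL that are independent of CSPN progression and which may occur shortly after treatment initiation". The NQOL-DN model has a spline to accommodate this.

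Three analyses follow.

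- **M1** compares treatment effects by "plotting the estimated treatment effects on each outcome with their 95% confidence intervals", with bootstrap limits for ratios of effects. Its two reading rules are "Concordant effects for IENFD and a particular clinical endpoint will suggest possible mediation of the treatment effect on the clinical endpoint through IENFD", and "discordant effects will suggest IENFD did not play a major role (i.e. was not clinically relevant").
- **M2** regresses change in the clinical endpoint on IENFD slope, controlling for arm.
- **M3** estimates the proportion of the treatment effect explained by IENFD slope.

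The plan describes M1's treatment effects as free of confounding because they compare randomized groups, and warns that M2 and M3 are not. It does not define discordance, and it has no rule for the case where the three analyses disagree.

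**The concern.** The parenthesis in the discordance rule treats two different statements as one. The first is that IENFD did not account for this drug's net effect on an endpoint. The second is that a change in IENFD does not matter to patients. The secondary objective asks about the second. M1 speaks, at best, to the first.

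Three situations produce discordance without bearing on clinical relevance:

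1. A direct effect opposes a real IENFD-mediated benefit.
2. A direct effect moves the endpoint while IENFD does not change.
3. One of the two estimates is imprecise.

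The first is conceivable here. Section 8 lists paresthesias, fatigue, nausea and memory problems among events seen at the study dose, and it notes that symptoms can have mixed origins: "In the setting of this study, paresthesias may also be related to the underlying disease (CSPN), or nerve regeneration". NQOL-DN has a symptoms subscore.

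Randomization makes each M1 effect estimate valid. It does not validate a verdict on mediation or relevance drawn from comparing them. At stake is a prespecified sentence that could wrongly count against IENFD when the measure is judged for later use.

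**Working it through.** **1. Inputs from Section 10, items e and f.** 125 randomized, 12% loss, two-sided alpha 0.05, 80% power for each co-primary. Detectable differences: 0.47 fibers/mm/year for IENFD slope and 7.9 NQOL-DN points over 96 weeks. SD of NQOL-DN change 16.4; baseline to follow-up correlation 0.60 (the upper limit given). Correlation between IENFD and NQOL-DN -0.30. Higher NQOL-DN is worse, so this is +0.30 when both are scored as benefit. I apply it to the two effect estimates.

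**2. Reproducing the plan's NQOL-DN figure.** Evaluable per arm: 125 × 0.88 / 2 = 55. ANCOVA residual SD: 16.4 × √((1 + 0.60)/2) = 14.67. SE of the difference: 14.67 × √(2/55) = 2.80 points. Power at 7.9: Φ(7.9/2.80 − 1.96) = 80.6%. The figure reproduces. The IENFD variance components are not printed, so that calculation cannot be rebuilt; 80% power at 0.47 implies SE = 0.47/2.80 = 0.168 fibers/mm/year.

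**3. M1 under stated scenarios.** The estimates are bivariate normal with the SEs above and correlation 0.30. Total NQOL-DN effect = indirect + direct. The documents give no sizes for the indirect and direct parts; these are assumptions, with positive meaning benefit.

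| True IENFD effect | Indirect | Direct | Total | Opposite signs | Significant benefit on one endpoint only |
|---|---|---|---|---|---|
| 0.47 | 7.9 | 0 | 7.9 | 0.5% | about 27% |
| 0.47 | 4.0 | 0 | 4.0 | 8% | 57% |
| 0.47 | 7.9 | −7.9 | 0 | 50% | 78% (IENFD only) |
| 0.47 | 4.0 | −7.9 | −3.9 | 92% | 80% (IENFD only) |
| 0 | 0 | +7.9 | 7.9 | 50% | 78% (NQOL-DN only) |

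Row 1: with 80% power on each endpoint, both are significant in 66.6% of trials, so exactly one is significant in 0.80 + 0.80 − 2 × 0.666 = 26.8%. With zero correlation this is 2 × 0.80 × 0.20 = 32%. Using 80.6% for NQOL-DN gives 26.5%.

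Row 3: IENFD is significant in 80%, and both show significant benefit in about 2.4%, leaving about 78%. IENFD matters to patients by construction, yet the discordance rule points the other way.

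Row 5: the pattern is the same whatever the link between IENFD and quality of life, because IENFD has not moved.

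**4. What M2 does in a cancelled case.** Take indirect +4.0 and direct −4.0, with no confounding. The true coefficient is 4.0/0.47 = 8.51 points per fiber/mm/year. A simulated regression of NQOL-DN change on IENFD slope and arm, with 55 per arm, returns about 8.5. Power runs from 43% to 100% for an assumed between-patient slope SD of 0.3 to 1.2, treating true slopes as known. Conditioning on arm removes the direct drug effect that misleads M1.

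**5. What M3 does there.** The proportion explained is one minus the ratio of adjusted to unadjusted treatment effect. When the total effect is near zero the denominator is near zero and the proportion is unstable. For a null clinical effect the plan itself names only M1 and M2 as informative.

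**The case against.** The language is softer than a quick reading suggests. Discordance is said to suggest, not to show; direct effects are said to be possible, not established; the objective is exploratory; and the concordance rule speaks only of possible mediation. All of that stands. The possibility of direct effects is nevertheless enough to break the inference, and the parenthesis itself is not hedged in the same way.

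The plan also does not leave direct effects unattended. M2 conditions on arm and is given the task of interpreting the IENFD slope clinically. M3 isolates the effect remaining after adjustment, and both are repeated on the NQOL-DN subscales. A reader might infer that the secondary objective stands or falls on M1, or that M1 alone would cause IENFD to be dropped as an endpoint. The documents support neither: nothing gives M1 that role, and the Go/No-Go rule uses the two effect estimates, not M1's interpretation.

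The magnitudes depend on an undefined term. Judged by opposite signs, chance discordance at the design effects is negligible. The cancellation figures need an assumed direct effect as large as the indirect one, and the 78% is close to a restatement of IENFD's 80% power. Nor do the documents show that side effects would worsen NQOL-DN: Section 8 calls paresthesias typically mild, and the crossover trial cited in Section 10.1.1 reports improved total NQOL-DN on topiramate. That does not exclude masking, but it is not evidence for it.

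Finally, a reader might conclude that M2 should replace M1. The plan's own warning that M2 can be confounded argues against making it the sole basis.

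**Conclusion.** The concern holds as a fault in one interpretive rule. Under the plan's own framework, discordant total effects do not imply that IENFD change is clinically irrelevant. They imply at most that IENFD does not explain the net drug effect on that endpoint, and imprecision can produce them too.

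How often the rule would mislead cannot be fixed from the documents. The cancellation and chance figures are illustrations that rest on the plan's stated power, the 0.30 correlation, assumed direct and indirect effects, and a chosen definition of discordance. The move from 27% to 0.5% with the definition alone is a reason to define the term.

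The existence of M2 and M3 limits the damage but does not remove it. The plan credits M1's estimates with freedom from confounding, cautions about the other two, and leaves a disagreement unresolved, so a reader could defer to M1 where its reading rule is weakest. No printed figure is wrong.

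**What to change.** In Section 10, item g on the clinical meaning of IENFD change:

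1. Delete the parenthesis that equates discordance with lack of clinical relevance.
2. Define discordance (by sign, confidence interval or ratio of effects). State that it may reflect direct drug effects or imprecision and is not evidence against the clinical relevance of IENFD.
3. Keep the hedged wording on possible mediation, and add that concordance can also arise from parallel direct effects.
4. State that the conclusion on clinical meaning is drawn from M1 read together with the M2 coefficient, including when they disagree, and keep the confounding caveat.

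These are wording changes and need no new data.

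Optionally, as a sensitivity analysis, report the M2 coefficient in the placebo arm, where there is no drug effect, beside the pooled treatment-adjusted one. This costs one further fit of a joint model in about 55 completers. Halving the sample widens the interval by roughly √2 = 1.4, and confounding between IENFD slope and clinical change remains.
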